5.7.1.4.2 Neutralizing anti-bimekizumab antibody

For confirmed ADA_b positive samples, NAb will be assessed using IL-17AA-specific and IL-17FF-specific assay methods. NAb results will be positive or negative to each specific NAb assay or both.

Any NAb results derived from samples with drug concentrations higher than the drug tolerance limits of the IL-17AA-specific and the IL-17FF-specific NAb assays (100µg/mL) will be labeled 'inconclusive'. All inconclusive results will be regarded as missing.

In addition to the ADA_b classifications, participants may also receive an overall neutralizing (NAb) classification for each NAb assay separately, inclusive of Baseline and post-Baseline results, on the NAb assay results:

- NAb negative: No NAb positive samples for IL-17AA and IL-17FF at Baseline or post-Baseline. This group will also include subjects who have only 1 missing sample and all other available samples during the period of interest are negative. Study participants who are NAb negative will be classified as follows:
 - ADA_b positive / NAb negative: ADA_b positive subjects who are 1) NAb negative for all available ADA_b positive samples or 2) with only one missing NAb sample and all other evaluated ADA_b positive samples are NAb negative.
 - ADA_b negative: if the subject has all the samples as ADA_b negative or only one missing/inconclusive sample with all other available samples as negative ADA_b.
- NAb positive: One or more positive samples (IL-17AA positive, IL-17FF positive, or both) at Baseline or post-Baseline (regardless of missing samples). Study participants who are NAb positive will be further classified as follows:
 - Positive for IL-17AA only: one or more positive samples for IL-17AA at baseline or post-baseline. No positive samples for IL-17FF.

- Positive for IL-17FF only: one or more positive samples for IL-17 FF at baseline or post-baseline. No positive samples for IL-17AA.
- Positive for both IL-17AA and IL-17FF: one or more positive samples for both IL-17AA and IL-17FF at baseline or post-baseline.
- NAb Missing: >1 relevant NAb samples are missing/inconclusive and other available NAb samples during the period of interest are negative. Study participants who are NAb missing will be further classified as follows:
 - ADA b missing/NAb missing
 - ADA b positive/NAb missing (missing or insufficient sample left for NAb testing)

5.7.1.4.2.1 Analysis

The following table and listing will be produced, but may not be produced in the Final CSR.

The listing will be sorted by weight-categorized dose group and will summarize the following information for each participant assessed for NABs:

- Visit
- Study week since first bimekizumab dose
- Sampling date and time
- Time since previous dose (weeks)
- The corresponding bimekizumab plasma concentration level at each visit (µg/mL)
- ADA b titer at each visit
- IL-17AA NAb status and corresponding IL-17AA signal/negative control result
- IL-17FF NAb status and corresponding IL-17FF signal/negative control result
- Value excluded from PK summaries (Y/N)

The summary table will display the overall NAb categories, based on data from Baseline up to Week 16, Week 20, Week 124 and SFU. The data from weight-categorized dose groups that contain a low number of participants may be combined, presenting Dose A total, Dose B total and across all participants. The table would provide the following overall summary statistics by weight-categorized dose group:

- Total number and percentage of overall ADA b positive, ADA b negative and ADA b missing participants (including the baseline value)
- Number and percentage of NAb negative participants, as defined in Section 5.7.1.4.2.
- Number and percentage of NAb positive participants, as defined in Section 5.7.1.4.2.
- Number and percentage of NAb missing participants, as defined in Section 5.7.1.4.2.

In addition, two figures (side by side) summarizing efficacy response (PASI90) versus time for each dose group (BKZ Dose A and BKZ Dose B) by NAb status (ADA b negative, NAb positive, ADA b positive / NAb negative, missing) will be created. If ≥95% of subjects are included in the non-missing groups, the missing group will not be displayed in the figure. The analyses will be

repeated for IGA0/1. The data will also be presented in a tabular format. Both NRI and OC will be presented.

The analysis of treatment emergent adverse events will be summarized by NAb status using the following categories for the All Periods (Initial Treatment Period and OLE Period) summaries:

- ADA b negative
- NAb negative
- NAb positive

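### The NAb rule sets no minimum number of evaluable results, so a participant whose only ADAb-positive sample has no NAb result is labelled NAb negative or fits no class

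*SAP*

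**What the plan says.** All of the rule is in SAP 5.7.1.4.2.

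- **Which samples are tested.** For confirmed ADAb "positive samples, NAb will be assessed using IL-17AA-specific and IL-17FF-specific assay methods".
- **Inconclusive results.** A NAb result from a sample with drug above 100 µg/mL is inconclusive, and "All inconclusive results will be regarded as missing".
- **NAb negative, basic condition.** "No NAb positive samples for IL-17AA and IL-17FF at Baseline or post-Baseline".
- **NAb negative, allowance.** "This group will also include subjects who have only 1 missing sample and all other available samples during the period of interest are negative".
- **Sub-class ADAb positive/NAb negative.** The first limb takes participants whose available ADAb-positive samples are all NAb negative. The second takes those "with only one missing NAb sample and all other evaluated" ADAb-positive samples NAb negative.
- **NAb missing.** "NAb Missing: >1 relevant NAb samples are missing/inconclusive and other available NAb samples during the period of interest are negative". One of its sub-classes is ADAb positive/NAb missing, which the SAP explains as "missing or insufficient sample left for NAb testing".

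SAP 5.7.1.4.2.1 carries the classes into a table (for example "Number and percentage of NAb negative participants, as defined in Section 5.7.1.4.2"), into PASI90 and IGA 0/1 displays by NAb status, and into a TEAE summary with three categories: ADAb negative, NAb negative and NAb positive. SAP 5.7.1.1 repeats the plasma concentration summaries by overall NAb status. Protocol 8.9.1 says only that confirmed positive samples are characterized further for neutralization; it gives no participant-level rule.

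**The concern.** Tolerating one missing result is reasonable when many results remain. The same tolerance appears in the overall ADAb rule (SAP 5.7.1.4.1.2), where the base is every scheduled sample: Baseline plus six visits through Week 20. For NAb the base shrinks to the ADAb-positive samples, and a participant may have only one. If that one result is missing, the allowance uses up all the data and a label is given with nothing behind it.

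The documents show three ways this can happen:

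- Too little sample is left for NAb testing.
- Drug in the sample is above 100 µg/mL. An ADAb-positive call carries no concentration condition (SAP 5.7.1.4.1.1), so such a sample can be ADAb positive yet NAb inconclusive.
- The sample is screen positive without a confirmatory result. SAP 5.7.1.4.1.1 counts it as ADAb positive, but NAb is run on confirmed positives.

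NAb status is also derived over short periods (to Week 16 and to Week 20), when a single positive sample is more plausible.

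At stake is what the NAb negative group means. A reader takes it as participants whose antibodies were tested and did not neutralize. In the TEAE summary, which has no missing column, an untested participant's events would be reported as NAb negative.

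**Working it through.** The plan states no figure for this rule, so there is nothing to reproduce. The check applies the rule to every possible record and then sizes the effect under stated assumptions.

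**Step 1. Apply the rule.** Take participants with 1 to 4 ADAb-positive samples and no NAb-positive result. With 0 or 1 result missing the class is NAb negative; with more than 1 missing it is NAb missing. Records with nothing missing are all NAb negative. The others are:

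| ADAb-positive samples | NAb results missing | NAb results evaluated | Class |
|---|---|---|---|
| 1 | 1 | 0 | NAb negative |
| 2 | 1 | 1 | NAb negative |
| 2 | 2 | 0 | NAb missing |
| 3 | 1 | 2 | NAb negative |
| 3 | 2 | 1 | NAb missing |
| 3 | 3 | 0 | NAb missing |
| 4 | 1 | 3 | NAb negative |
| 4 | 2 | 2 | NAb missing |
| 4 | 3 | 1 | NAb missing |
| 4 | 4 | 0 | NAb missing |

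Only the first row gives NAb negative with no evaluated result. It holds the same information as the rows 2/2, 3/3 and 4/4, namely none, but gets the opposite label. It cannot reach ADAb positive/NAb missing because that sub-class sits under the more-than-one condition.

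**Step 2. Apply the proposed rule.** If ADAb positive/NAb negative also needs at least one evaluated negative, and NAb missing also takes anyone with no evaluable result, the first row moves to NAb missing. Every other row keeps its class.

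**Step 3. Size.** The plan has 40 participants (SAP 3). The rates below are assumptions, since the documents give none: ADAb positive 20-50%; a single positive sample among those 30-50%; NAb result missing or inconclusive 5-20%.

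- Low end: 40 × 0.20 × 0.30 × 0.05 = 0.12 participants
- Midpoints: 40 × 0.35 × 0.40 × 0.125 = 0.7 participants
- High end: 40 × 0.50 × 0.50 × 0.20 = 2.0 participants

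**Step 4. Effect on the NAb-positive figures.** Moving a participant from NAb negative to NAb missing leaves the number of NAb-positive participants unchanged. Their share of the dose group, or of all ADAb-positive participants, is unchanged too, because neither denominator moves.

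**The case against.** The strongest reply is that the SAP's intent is visible. Speaking of all other available or evaluated samples presupposes that at least one exists, and the SAP has a sub-class that describes the untested participant. On that reading the NAb negative label does not follow. This stands in part: the label depends on reading a condition about other samples as met when there are none. It does not rescue the rule. Such a participant still has no NAb-positive sample and still falls short of the threshold for NAb missing, so the alternative is to belong to no class. If ADAb-negative visits count as the other available samples, the result is NAb negative again.

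One could also say that a lone missing result is called negative by convention. SAP 5.7.1.4.1.4 does this for the Baseline sample in the cumulative ADAb status. There, however, the one-sample case is addressed explicitly; in the NAb rule it is not.

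The case may be rare. Protocol 8.6 splits each plasma sample into six aliquots, two of them for NAb (one primary, one back-up), which reduces the insufficient-volume route. Samples at dosing visits are taken before dosing (Table 1-1 note n, Table 1-2 note l), and half the participants are assigned 64 mg or 32 mg, so concentrations above 100 µg/mL may be uncommon. The documents report no concentrations, so the frequency is unknown. These points stand and favour the lower part of the range.

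A reader might infer that one misplaced participant shifts a subgroup's PASI90 rate by 10 points or more. Removing one member from a group of n moves its rate by at most 1/n, so 10 points needs a group of 10 or fewer and a member whose outcome differs from the rest. With 9 responders of 10, removing a responder gives 8/9 = 88.9%, a shift of 1.1 points.

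Finally, all analyses are descriptive (SAP 2). The NAb table and listing may be left out of the final CSR (SAP 5.7.1.4.2.1). Where the listing is produced, it shows NAb status by visit, so an untested sample could be seen.

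**Conclusion.** The rule is wrong as written in one pattern: exactly one ADAb-positive sample with a missing or inconclusive NAb result. The literal rule gives ADAb positive/NAb negative and a stricter reading gives no class; neither is the missing class that the SAP itself describes. This follows from the wording alone and needs no assumed rate.

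The consequence is limited. The NAb negative group can include participants with no neutralization result, in the NAb table and in the efficacy, PK and TEAE displays by NAb status. The expected number is about 0.1 to 2 of 40, with the top of the range requiring all three assumed maxima together. Analyses not split by NAb status, including the main concentration summaries and the secondary efficacy endpoints, are untouched.

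A reader might go further and infer that NAb incidence is understated. The documents do not support that. SAP 5.7.1.4.2.1 plans numbers and percentages of NAb-positive, NAb-negative and NAb-missing participants and sets no tested-only denominator. Nor does an untested participant have to be truly NAb positive; the fault is that the negative label has no evidence behind it.

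**What to change.** In SAP 5.7.1.4.2:

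- **ADAb positive/NAb negative:** require at least one evaluable negative NAb result on an ADAb-positive sample, none positive, and at most one missing. Apply the same condition to ADAb-positive participants in the general one-missing allowance, so that class and sub-class agree.
- **NAb missing:** extend it to more than one relevant NAb sample missing or inconclusive, or no evaluable NAb result on any ADAb-positive sample. This makes the existing ADAb positive/NAb missing sub-class reachable for the participant in question.
- **ADAb negative sub-class:** leave it unchanged. Those participants have no samples for NAb testing, so a minimum must not be imposed on them.

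The cost is a short wording edit and a small programming change. The NAb missing count may rise slightly. Because the TEAE summary by NAb status has no missing category, a relabelled participant would drop out of it, as other NAb missing participants already do; a footnote with the number excluded would cover this.

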5.6.2.2 AE summaries

The following AE summaries for participant incidence and event number will be provided by weight-categorized dose group for the Initial Treatment Period, OLE Period, and the combined periods. Selected summaries as noted will report exposure adjusted rates. An overall summary of the AEs will also be provided. AE tables will summarize Dose A (320mg, 160mg, Total), Dose B (all) and All Participants on one page; the subsequent page will contain Dose B (64mg, 32mg, Total), Dose A (all) and All Participants.

- Summary by system organ class (SOC), HLT, and preferred term (PT):
 - Any TEAE (with exposure-adjusted rates)
 - Serious TEAE (with exposure-adjusted rates)
 - TEAEs leading to withdrawal from the study (with exposure-adjusted rates)
 - TEAE leading to discontinuation of investigational medicinal product (IMP) (with exposure-adjusted rates)
 - TEAE leading to death
 - Related TEAE
 - Related serious TEAE
 - TEAE for safety topics of interest and safety topics closely monitored (with exposure-adjusted rates)
- Summary by relationship, SOC, HLT, and PT
 - Any TEAE
 - TEAE leading to death (for EudraCT reporting purposes)
- Summary by maximum relationship, SOC, HLT, and PT
 - Any TEAE
- Summary by severity, SOC, HLT, and PT
 - Any TEAE
- Summary by maximum severity, SOC, HLT, and PT
 - Any TEAE

Ordered and subset of AE summaries will be reported in a separate table to facilitate review when needed. Examples include:

- Serious TEAE by SOC and PT
- Nonserious TEAE by SOC and PT above reporting threshold of 5%

- Any TEAE by decreasing frequency of PT

The following summary will be provided for antibody data (Section 5.7.1.4.1.6 and Section 5.7.1.4.2.1):

- Incidence of TEAEs per 100 participant years by SOC, HLT, and PT and by time of onset relative to ADAb status. Note: Only presented for combined Initial Treatment Period and OLE Period.
- Incidence of TEAEs per 100 participant years by SOC, HLT, and PT and by time of onset relative to NAB status. Note: Only presented for combined Initial Treatment Period and OLE Period.

The following AEs will be listed separately:

- Any TEAE with onset at day 1
- Any TEAE related to TB including latent TB and IGRA tests

The following summaries will be produced for the Plain Language Summaries:

- Incidence of Drug-related TEAEs – Overview
- Incidence of Drug-related TEAEs by Preferred Term
- Incidence of Serious Drug-related TEAEs by Preferred Term

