5.7.1 Other endpoints and parameters

5.7.1.1 Pharmacokinetics

The primary variable of this study is plasma bimekizumab concentrations, assessed at Baseline, Week 1, Week 4, Week 8, Week 12, Week 16, Week 20, Week 40, Week 64, Week 88, Week 112, Week 124, EDV, and SFU Visit. Pharmacokinetic analyses will be performed in the PK-PPS. Summary tables will be created for the Initial Treatment Period for all participants in PK-PPS, and across All Periods (Initial Treatment Period + OLE Period) summaries for all participants that are in both the OLS and PK-PPS (i.e. all study participants who receive at least 1 dose of IMP at or after Week 20 in the OLE Period and who have at least 1 quantifiable plasma concentration without important protocol deviations that would affect the concentration in the OLE Period).

Bimekizumab plasma concentrations will be summarized with descriptive statistics and plotted for each weight-categorized dose group, at each scheduled visit. Summaries of bimekizumab plasma concentration over time will be reproduced with rounding to 1 decimal place and may be used for Plain Language Summaries. These tables and figures will be repeated by cumulative anti-bimekizumab antibody status (See Section 5.7.1.4.1.4) and by overall NAb status (See Section 5.7.1.4.2). Bimekizumab plasma concentrations summaries will be based on observed values, with each sample falling within the time window rules described below. No imputation will be used for missing data. If plasma concentration measurements are below the level of quantification (BLQ), then for calculation of the derived statistics the result will be set to $\frac{1}{2}$ of the LLOQ. Descriptive statistics including geometric mean, geometric coefficient of variation, and geometric mean 95% CI (if applicable) will be calculated if at least two-thirds of the values of interest are above the LLOQ and $n \geq 3$. If this is not the case, only median, minimum, and maximum will be presented.

All PK concentrations will be listed.

By-visit summaries and figures of plasma concentrations will exclude data points where protocol deviations and/or deviation from scheduled dose and sample collection window are expected to impact drug exposure. The protocol deviations will be reviewed by the Quantitative Clinical Pharmacology (QCP) representative and a decision about impacted data points will be made prior to generating summary statistics.

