- AEs starting before first ADA_b positive result
- AEs starting on or after first ADA_b positive result
- AEs for participants who were always ADA_b negative

A study participant's associated time at risk will be split into the time before the first positive result and on or after the first positive result. If a study participant has multiple reports of the same AE (ie, those which code to the same preferred term) emerging both prior to first ADA_b positive result and after ADA_b positive result, both events will be summarized in the table in the appropriate column.

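### The NAb adverse-event table has overlapping categories and no onset rule, although SAP 5.6.2.2 plans it by onset; concentrations are grouped by overall rather than cumulative NAb status

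*SAP*

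**What the plan says.** Four parts of the SAP bear on this.

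- **Definition of status (5.7.1.4.2).** NAb negative is a parent class: "Study participants who are NAb negative will be classified as follows", and the two sub-classes are ADAb positive/NAb negative and ADAb negative. The latter applies "if the subject has all the samples as ADA_b negative or only one missing/inconclusive sample", with the remaining samples negative. NAb positive means: "One or more positive samples (IL-17AA positive, IL-17FF positive, or both) at Baseline or post-Baseline (regardless of missing samples"). No onset date enters the definition.
- **Outputs (5.7.1.4.2.1).** The overall NAb categories are derived for four windows, "based on data from Baseline up to Week 16, Week 20, Week 124 and SFU". The PASI90 and IGA 0/1 figures use four exclusive groups: ADAb negative, NAb positive, ADAb positive/NAb negative, and missing. The adverse-event text is: "The analysis of treatment emergent adverse events will be summarized by NAb status using the following categories for the All Periods" summaries, followed by three categories only: ADAb negative, NAb negative, NAb positive.
- **Adverse-event list (5.6.2.2).** The same table is announced as TEAEs per 100 participant-years "by time of onset relative to NAB status", for the combined periods only, under an introduction that cites 5.7.1.4.2.1. For the parallel ADAb table, 5.7.1.4.1.6 states that a participant's "associated time at risk will be split into the time before the first positive result" and the time on or after it.
- **Concentrations (5.7.1.1).** Tables and figures are repeated by cumulative ADAb status and "by overall NAb status (See Section 5.7.1.4.2"). Under 5.7.1.4.1.4, cumulative ADAb status turns positive only from the first visit with a positive sample.

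**The concern.** These tables are meant to show whether neutralizing antibodies go with a different safety profile or lower exposure. The informative comparison for neutralization is NAb positive against participants who formed antibodies that did not neutralize. If the NAb-negative column also holds everyone who never formed antibodies, it mostly repeats the ADAb-negative column and that comparison is not displayed.

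Timing is the second issue. A participant classified by any positive sample in a window carries the NAb-positive label at visits before the antibody was detected. For concentrations this follows directly from the text. For adverse events the SAP gives two incompatible descriptions, and a programmer working from 5.7.1.4.2.1 alone could not build the table that 5.6.2.2 announces.

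**Working it through.** The plan gives no figure to reproduce here, so the check is one of definitions, with illustrations.

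**1. Overlap.** Let a = ADAb negative, b = ADAb positive/NAb negative, c = NAb positive, with none missing. By 5.7.1.4.2 the NAb-negative column holds a + b, so the three columns sum to a + (a + b) + c = N + a, and the ADAb-negative share of the NAb-negative column is a/(a + b). N = 40 is the planned minimum (SAP 3). The splits below are assumptions.

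| a / b / c | Columns | Total | a/(a + b) |
|---|---|---|---|
| 30 / 6 / 4 | 30, 36, 4 | 70 | 30/36 = 83% |
| 24 / 8 / 8 | 24, 32, 8 | 64 | 24/32 = 75% |
| 16 / 12 / 12 | 16, 28, 12 | 56 | 16/28 = 57% |

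With the four groups of the efficacy figures, the columns sum to 40 in every case.

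**2. Adverse events: the sections side by side.** SAP 5.6.2.2 requires onset relative to NAb status. SAP 5.7.1.4.2.1 lists three participant-level categories with no before or after. SAP 5.7.1.4.1.6 gives ADAb both the categories (before the first positive, on or after it, always negative) and the split of time at risk. Nothing equivalent exists for NAb.

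How much could turn on this, if the category list were followed as it stands? Take a participant who completes the study with the last dose at Week 120 (inferred from Q4W dosing, OLE dosing from Week 20 and the 120 weeks of active treatment in Protocol 4.1). With no change of dose level, SAP 5.6.1.1 to 5.6.1.3 give 141 days (Initial Treatment Period) + [(840 − 140) + 141] days (OLE) − 1 day = 981 days, and 981/7 = 140.1 weeks. The share of time at risk before onset is onset week/140.1:

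- Week 16: 16/140.1 = 11%
- Week 40: 40/140.1 = 29%
- Week 64: 64/140.1 = 46%
- Week 112: 112/140.1 = 80%

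If the event rate were 20 per 100 participant-years before onset and 40 after (assumed), a column pooling all that time would show 20 × share + 40 × (1 − share): 37.7, 34.3 and 30.9 for onset at Weeks 16, 40 and 64.

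**3. Concentrations.** The sampling visits in 5.7.1.1 before Week 88 are Baseline and Weeks 1, 4, 8, 12, 16, 20, 40 and 64. In an All Periods table that uses the longest window, a participant first NAb positive at Week 88 sits in the NAb-positive group at all nine. Under the cumulative rule used for ADAb, that participant would be NAb positive from Week 88 only. Rows from Week 88 on are the same under both rules. Within the Initial Treatment Period the mechanism is the same but shorter: first positive at Week 16 labels Baseline and Weeks 1 to 12 as NAb positive.

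**The case against.** **The category list may be shorthand.** NAb is assayed only in ADAb-positive samples, and the paragraph just before the list uses exclusive groups, so the author may have meant ADAb positive/NAb negative for the second column. That is plausible, but the text does not say so and the written definition says otherwise. It is also fair that nested columns appear elsewhere in this SAP (320 mg, 160 mg, Dose A all), and that counts for the missing group follow by subtraction. Subtraction works only if the reader knows which reading was programmed.

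**A reader might infer that the plan credits pre-onset adverse events to NAb.** The documents do not support that as settled, because 5.6.2.2 plans the table by onset. What stands is a contradiction between two sections and a missing time-at-risk rule.

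**A reader might infer that NAb status is always assigned over the whole study.** That is too broad: four windows are defined, two of them ending at Week 16 and Week 20. The SAP does not say which window each concentration table uses, so the Week 88 example applies to All Periods tables only.

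**A reader might infer a bias toward no effect.** This is not shown. If low early exposure preceded antibody formation, grouping by later status could widen the contrast in concentrations.

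**The consequence is small.** All analyses are descriptive (SAP 2). The NAb listing gives concentration and NAb status by visit, and population PK and exposure-response have separate plans. SAP 5.7.1.4.2.1 says the NAb table and listing may not be produced in the final report; whether this covers the TEAE table is unclear. These points limit the impact but do not repair the text.

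**Conclusion.** Wrong as written, with limited impact. Three things follow from the SAP's own text: the TEAE categories overlap and omit NAb missing; 5.6.2.2 and 5.7.1.4.2.1 disagree on whether the table is by onset, with no NAb rule for time at risk; and concentrations are grouped by overall NAb status within a window while ADAb is cumulative.

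The overlap rests on reading 5.7.1.4.2 literally. The illustrative sizes (columns summing to 56 to 70 for 40 participants, 11% to 80% of time at risk before onset) rest on assumed splits and onset times, and the second range applies only if the participant-level categories are used as listed. The direction and size of any distortion in the actual results cannot be stated from these documents.

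**What to change.** - **SAP 5.7.1.4.2.1:** replace the three TEAE categories with the exclusive groups of the efficacy figures: ADAb negative; ADAb positive/NAb negative; NAb positive; missing. Divide NAb positive into events before, and on or after, the first NAb-positive sample, and split time at risk at the same date, as for ADAb. Participants NAb positive at Baseline then fall wholly in the second part.
- **SAP 5.6.2.2:** keep the onset wording and confirm that it describes this table, so that the two sections agree.
- **SAP 5.7.1.1:** use cumulative NAb status by visit for the concentration tables and figures, or show it beside overall status, and state which window each table uses if overall status is kept.

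The cost is SAP wording and reprogramming of a few tables, with no new data. Some cells will be small, since about 40 participants are spread over five columns by SOC, HLT and PT.
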